Topography is the study of consumption behaviors in extensive details in either laboratory or natural settings.⁹ Data can be obtained objectively and noninvasively through a topography device or videotaping. This approach been widely applied to tobacco research in investigating puffing behaviors (e.g., puff duration, puff volume, and puff speed). The characteristics of puffing behavior measured by topography such as puff speed and puff duration are shown to be reliable indicators for individual differences,¹⁰⁻¹³ nicotine dependence,^{11,14} and abstinence after quitting.¹⁵

Despite its utility, alcohol topography has not been as well-established as smoking topography. Alcohol topography measures have been used successfully as alternate measures of alcohol self-administration in human laboratory studies.^{16,17,24} Despite calls for the use of alcohol topography to expand (e.g., as a longitudinal predictor of drinking outcomes)²⁵ these research efforts have not yet materialized. To explore the potential of using alcohol topography as a noninvasive objective measure of alcohol drinking behavior and the possibility of using the identified behavioral pattern as an indicator for alcohol use disorder.

4. Preliminary Study

The video-assisted topography method was developed as an indicator of nicotine dependence by our group in previous research.¹⁸ The procedure involves videotaping one smoking episode of a whole cigarette and coding the video frame by frame to generate parameters of puffing behaviors (e.g., puff speed, puff duration, puff interval, and etc.). The temporal pattern of each parameter is plotted using time (in seconds) as the x-axis, and fitted to both linear and nonlinear (i.e., fold catastrophe) models. Results from the smoking topography study showed that the indicators derived from the fitted catastrophe model were significantly associated with self-reported nicotine dependence scores, especially DSM-IV criteria. This study provided an impetus for us to explore the potential of using the same method to develop topographic indicators for alcohol use disorder.

[figure not shown]
5. Specific Aims

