The overall goal is to pilot test and establish a procedure for video-assisted alcohol topography and explore its utility as an indicator of alcohol use disorder. Our specific aims include the following: (1) characterize drinking behavioral patterns by converting videotaped drinking episodes into various drinking related parameters (e.g., sipping frequency, sipping intervals, sipping duration, rest duration, sipping amount); (2) compare drinking behavioral patterns across groups defined by drinking status (social vs. heavy drinkers) and mental health status (elevated vs. non-elevated depressed mood); and (3) use advanced nonlinear modeling to quantify the behavioral pattern and to derive potential indicators for alcohol use disorder.

6. Research plan

Overview

There are 4 phases to this study: 1) pre-screening by phone; 2) in-person screening appointment; 3) the first alcohol drinking session with videotaping; and 4) follow-up appointment for retest. The figure below gives a timeline of the steps involved in the study. Each alcohol drinking session including all testing will require 3-4 hours.

Participants

Recruitment: Participants will be recruited through recruiting flyers (Attached) posted on the UF campus and vicinity, along with ads posted on online classified sites such as Craigslist and newspapers. Prospective participants who see one of these

advertisements and are interested in the study will contact the study initially via telephone, text, or email message. Study staff will answer any questions and conduct a preliminary phone screen among those who would like to pursue study participation.

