Laboratory setting: The videotaped drinking session will take place in the simulated bar laboratory, located in Yon Hall North on the UF campus. This laboratory has been established to maximize ecological validity by simulating an actual bar. Two protocols have been approved by IRB01 to take place in this laboratory setting (IRB201500990, 201600614). It includes the drinking bar itself (seats 3 people), alcohol brand signage, television, glassware, music, and a beer tap (nonoperational). A high-definition camcorder (Sony FDR-AX53, DVD format, 100 frames/s or equivalent) will be set up in the wall cabinet after the participant is seated at the bar. The distance from the camcorder to participants is around 1.5 meters. The camcorder will be adjusted each time before videotaping to focus on the upper body of the participant to capture the detailed drinking behaviors. A digital scale (IDAODAN nutrition food scale, 5kg max, 1g/0.1oz accuracy) will be set up in front of the participant on the bar counter. The scale is equipped with wireless bluetooth technology that automatically uploads measurement to the research computer. A coaster will be placed on top of the scale. Participants will return their drink to the coaster on top of the scale after each sip. Readings from the scale will not be observable to participants.

Videotaped drinking session: An initial alcohol drinking session will take place following in-person screening. Participants will be asked not to drink any alcohol on the day of an alcohol drinking session prior to coming to the lab for the session. They will also be asked to abstain from food during the 4 hour period leading up to their session.

Transportation will be provided by the study to and from the research facility using either a university-owned vehicle or a commercial transportation service. Participants can be

picked up from any convenient location in the Gainesville area though transportation after the session must be taken directly home only. Participants within an 0.5 mile radius of the research facility may be walked to and from the facility by a study staff member rather than driven.

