When participants arrive, they will have a short rest period during which they will be asked to consume a 150-200 calorie snack. After they consume the snack, the alcohol drinking period will begin. This part of the session will take place in a laboratory space that has been built and decorated to look like an actual bar. There will be a camcorder set up in the lab to record the whole drinking session. Beer will be the only beverage that we provide. We will provide several common brands with similar calorie (125-150) and alcohol level (approximately 4.5% ABV) for the participants to choose from (e.g., Yuengling lager, Yuengling black and tan, Smithwicks Ale). We will pour the beer of their choice into a standard glass for them to drink. The participants will be asked to drink as they usually do. They will be requested to put the glass on a food scale that we provide throughout the drinking process whenever they are not holding it.

After completing the first beer, they will take a 30 minute break before they can drink the second beer. It must be the same brand as the first beer. During the break, they may take part in recreational activities (e.g., watching television, playing games). They will be allowed to read magazines but will not be permitted to complete work during the alcohol drinking period (either academic or for a job). When they are ready after the required break time, they can start drinking the second beer. The request will be the same for them as for the first beer, and only the same type of beer as their first drink will be provided to them.

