Participants may be selected for a follow-up appointment for the retest after 1-2 weeks, which includes repeating the same procedure alcohol drinking session procedures as their first appointment. To make data comparable, only the same type of beer as their first drinking session will be provided to them. At the outset of this pilot study, all participants will be invited for a second session, however the study Co-PIs reserve the right to limit participation to one alcohol drinking session per individual subsequently based on limitations with preliminary study funding and/or time limitations in terms of obtaining preliminary data in support of subsequent grant applications.

Compensation for drinking session:

Participants will receive \$40 for completing each drinking session, provided they complete all study procedures and remain in the laboratory until their breath alcohol level declines to .02%. Participants leaving before this point will be given a prorated payment based on a rate of \$10 per hour. Those departing before their breath alcohol declines to a safe level during the first alcohol drinking session will be excluded from the second session.

List of instruments

Pre-Screening phase:

Demographic information: Basic demographics will be collected, including age, gender, race/ethnicity, height and weight.

Frequency and quantity of alcohol consumption: Four questions will be used to assess alcohol use: (1) number of days used alcohol in the past 30 days; (2) number of binge drinking (i.e., 5 or more drinks for men, 4 or more drinks for women) days in past 30 days; (3) highest number of alcoholic drinks consumed on any given day in the past 30 days; and (4) number of binge drinking days in the past year. Five response options will be given for each question

Frequency and quantity of cigarette smoking: Two questions will be used to assess (1) number of days smoked in the past 30 days and (2) the average number of cigarettes smoked per day on the days they smoke in the past month. Five response options will be given for each question

Preferences for different alcoholic beverages: One question will assess participants' preferences for beer, wine, and/or liquor, followed by questions asking on how many days respondents have consumed each type of alcohol in the past 30 days.

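### Does the looser wording of the participant request leave individual sip amounts unmeasured?

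*Combined protocol and SAP*

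**What the plan says.** The handling of the glass is described twice in section 6 of the protocol.

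- **Laboratory setting**, on the camera and scale: "Participants will return their drink to the coaster on top of the scale after each sip".
- **Videotaped drinking session**, on what participants are asked to do: they are to drink in their usual way and to "put the glass on a food scale that we provide throughout the drinking process whenever they are not holding it". For the second beer, "The request will be the same for them as for the first beer".

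Under Follow-up for retest, the second visit consists of "repeating the same procedure alcohol drinking session procedures as their first appointment", so whatever handling rule applies at the first visit applies again.

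On measurement, the drinking session text says "There will be a camcorder set up in the lab to record the whole drinking session". Section 5 (Specific Aims) sets the first aim as "converting videotaped drinking episodes into various drinking related parameters (e.g., sipping frequency, sipping intervals, sipping duration, rest duration, sipping amount". The third aim is to "use advanced nonlinear modeling to quantify the behavioral pattern". Section 4 (Preliminary Study) describes frame-by-frame coding of smoking videos, with each parameter plotted over time and fitted to linear and nonlinear models, and gives that work as the reason to explore "using the same method to develop topographic indicators for alcohol use disorder".

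The scale is the only weighing instrument described. No section says how to treat a weight drop that covers more than one sip.

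**The concern.** The two sentences do not ask for the same thing. A participant who lifts the glass, sips twice and sets it down has done what the session text requests but not what the set-up text describes. The scale then records one drop for two sips, and only their sum is known.

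Sipping amount is a named parameter, and the pilot exists to establish the measuring procedure. If only the looser request reached participants, some sip-level amounts would be missing under the first aim. Any model of amount over time under the third aim would rest partly on averages. That second step is an inference: the third aim does not name amount as a series to be fitted. A careless reading of one drop as one sip would also inflate mean sip amount.

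**Working it through.** There is no plan figure to reproduce. The check has two parts: whether the texts conflict, and what is lost if the looser one alone is followed.

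**1. Do the texts conflict?**

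| Behaviour | Set-up text | Session request |
|---|---|---|
| One sip, glass back on scale | met | met |
| Two sips in one hold, then glass back | not met | met |
| Glass put down off the scale | not met | not met |

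The set-up rule is the stricter of the two. Obeying it meets both, so there is no contradiction, and the plan followed as written gives one weight per sip.

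**2. What if only the looser request is followed?**

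The documents give no rate of multi-sip holds, so every rate here is an assumption. Let a share m of lifts contain two sips and the rest one.

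- Sips per lift = 1 + m.
- Share of sips without their own weight = 2m/(1 + m).
- Shortfall of weighings relative to sips = m/(1 + m).
- Weighings per beer, assuming 20 sips = 20/(1 + m).
- Mean sip amount if one drop is misread as one sip, relative to the truth = 1 + m.

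| | m = 0.10 | m = 0.30 | m = 0.50 |
|---|---|---|---|
| Sips without their own weight | 0.20/1.10 = 18% | 0.60/1.30 = 46% | 1.00/1.50 = 67% |
| Shortfall of weighings | 0.10/1.10 = 9% | 0.30/1.30 = 23% | 0.50/1.50 = 33% |
| Weighings per 20 sips | 18.2 | 15.4 | 13.3 |
| Mean if one drop is misread as one sip | 1.10 | 1.30 | 1.50 |
| Mean from total drop / video sip count | 1.00 | 1.00 | 1.00 |

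The last row is exact: total weight lost and number of sips are both observed, however the sips fall into holds.

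**3. Effect on a time trend and on spread.**

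This was simulated with 20,000 beers per value of m and 20 sips per beer. Assumed sip amount falls in a straight line from 24 g to 12 g, with a sip-to-sip SD of 6 g. Each sip in a two-sip lift is given the lift average.

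| | m = 0.10 | m = 0.30 | m = 0.50 |
|---|---|---|---|
| Slope relative to slope from individual sips | 0.999 | 0.996 | 0.995 |
| Slope understated by | 0.1% | 0.4% | 0.5% |
| Within-beer SD of amount reduced by about | 4% | 9% | 14% |

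**4. What is unaffected.** Sip frequency, interval, sip duration and rest duration come from the video and do not depend on the scale. Total intake is the overall weight change.

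**The case for a change.** The strongest case for a change is that the session text is the only place where the request to participants is set out, and it omits the per-sip return. Staff working from it would not ask for that return, and the omission carries through to the second beer and the retest. Video supplies the count and timing of sips but not each sip's weight within a hold. The loss falls on sip-to-sip spread and fine pattern, which a nonlinear model may use: the SD shrinks by 4% to 14% under the rates assumed above, even though the mean and slope survive. One added sentence would close the gap.

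Part of this stands. The wording does differ, and the plan gives no rule for sharing out a weight drop. The step from there to a defect does not hold, for four reasons.

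- The per-sip return is already in the protocol, and section 11 has sessions supervised by staff trained in this specific protocol.
- The session paragraph is a description and not a participant script. Section 8 mentions verbal and printed instructions whose full wording is not in the documents, so they settle the point neither way.
- Frame-by-frame coding of the kind described in section 4 lets an analyst count sips per lift. The inflated mean arises only if that count is ignored, which the plan nowhere proposes.
- Stressing a return after every sip has a price. It pulls against natural drinking in the simulated bar and could itself alter intervals and rest duration, which are also named parameters.

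**Conclusion.** No change to the plan is needed. The set-up text states the per-sip return unconditionally, the session text is compatible with it, and a study run to the document weighs every sip. The difference is one of drafting.

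If some participants nonetheless sip more than once per hold, the loss is confined to individual amounts within those holds and to the spread and fine pattern built on them. Total intake, mean sip amount from the video count and all timing measures stand, and a straight-line trend is understated by no more than 0.5% in the cases examined. The sensible handling is to divide the drop by the video-coded sips in that lift and treat the result as an average. An analyst holding both data streams would do this without being told.

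These sizes rest on assumed values: 10%, 30% or 50% of lifts with two sips, 20 sips per beer, amounts falling from 24 g to 12 g, and an SD of 6 g. None comes from the documents, and the true frequency of multi-sip holds cannot be derived from them. The finding that the two texts are compatible, and that totals, means and timing survive, does not depend on those values.

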General inclusion & exclusion criteria: Participants must be 21-55 years of age, able to read English and complete study surveys, report liking beer and consuming it at least once in the past 30 days, and report having consumed at least two alcoholic drinks on at least one day during the past 30 days (i.e., current drinkers). Participants will be excluded if their urine drug test indicates recent use of illegal drugs (except cannabis) and pregnancy for women. In addition women who report engaging in sexual activity with opposite sex partners without use of reliable birth control will be excluded. Participants will also be excluded for any of the following conditions: a history of medically-assisted detoxification; present with signs of current alcohol withdrawal; currently meet the severe threshold for alcohol use disorder according to DSM-5 (i.e., 6 criteria or more); currently meet DSM-5 substance use disorder criteria at any level (i.e., 2 or more criteria) for any substance besides alcohol; are currently seeking treatment for problem substance use; have engaged in intensive outpatient or inpatient treatment for substance use in the past 12 months; meet criteria for severe depression or have any serious psychological or medical history that contraindicates alcohol consumption; currently taking any medication that contraindicates alcohol use at the levels included in this study; and have BMI under 18.5 or over 35. Given that video recording is a critical aspect of the study, participants will be required to agree to video recording in order to take part in the study. Undergraduates enrolled at the University of Florida will be excluded from participating. Graduate and non-matriculating students will be allowed to participate as long as they are not enrolled in the College of Health and Human Performance.

Subgroup division: Participants will be further divided by drinking status (social vs. heavy drinkers) and mental health status (elevated vs. non-elevated depressed mood). This creates four combinations of subgroup category (2×2). Efforts will be made to recruit equal numbers of men and women in each of the 4 categories.

Sample size: As a pilot study, we will target enrollment of up to 40 participants (~10 in each subcategory as defined in the previous section).

Procedure

Pre-screening by phone:

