- a. *Drinking behaviors:* Past 30-day drinking behaviors and DSM-5 criteria for alcohol use disorder will be used as the basis for distinguishing social and heavy drinkers. The social drinker group will be those who (1) consume at least 1 but no more than 5 standard alcoholic drinks per week and (2) engage in infrequent binge drinking (i.e., 5 or fewer times per year, but allowing for 1 past interval of a maximum of 6 months' duration of up to twice weekly binge drinking). The heavy drinker group will be those who (1) consume at least 10 alcoholic drinks per week ; (2) engage in regular binge drinking (i.e., consume 5 or more drinks on one occasion or ≥ 4 for women 1 to 5 times on average per week); and (3) meet DSM-5 criteria for mild or moderate alcohol use disorder. These criteria are based on criteria outlined by King et al.¹⁹ The timeline followback (TLFB) interview will be used to obtain self-reports of drinking behavior with a focus on past-30-day behavior, however the extent to which recent drinking behavior resembles past-12-month and lifetime drinking behavior will be queried in order to make sure participants meet criteria for

one of these two categories. Those who drink but who did not clearly fall into one of these two groups will be excluded from participation.

- b. *Depression:* Patient Health Questionnaire (PHQ-2 and PHQ-9) will be used for depression screening. The non-elevated depressed mood group will be those who scored less than 3 on PHQ-2 (i.e., negative PHQ-2). Elevated depressed mood group will be those who scored 3 or more on the PHQ-2 (i.e., positive PHQ-2) and 5 or more on the follow-up PHQ-9. Those who scored 20 or more (i.e., severe depression) will be excluded from the study and offered local referral options for treatment.

Once the participants pass the breath alcohol and urine testing, and meet all the eligibility criteria, they will be scheduled for the first of two alcohol drinking sessions. Compensation for the in-person screening appointment will be \$10 for those deemed ineligible during the first hour of the appointment and \$20 for those who complete the two hour appointment, regardless of eligibility or interest in continuing with the study.

Videotaped drinking session:

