General questions regarding other inclusion/exclusion criteria: Two questions will list the other inclusion and exclusion criteria respectively, and ask participants whether or not any of the criteria pertain to them.

In-Person Screening

Withdrawal symptoms: The 10-item Clinical Institute Withdrawal Assessment for Alcohol (Revised) (CIWA-AR)²² will be used to assess severity of current withdrawal syndromes.

Depression: Patient Health Questionnaire (PHQ-2 and PHQ-9)^{23,24} will be used for depression screening.

Medical and psychiatric history: A medical and psychiatric history will be taken from all participants, which will cover the following conditions: hypertension, diabetes, high cholesterol, cardiac abnormalities, pancreatitis, renal insufficiency, cancer, pulmonary disease, thyroid conditions, history of head injury or other neurological problems, stomach or intestinal disorders and liver disease. Participants will also be asked whether they have ever been diagnosed with a psychiatric condition or received treatment for such a condition. Participants will be asked to report all medications, including over the counter medications and those that they are currently taking, including psychotropic medications. The Structured Clinical Interview for DSM-5 (First et al., 2015) will be used to classify patients according to the presence or absence of past or present alcohol and other substance use disorders.

Self-reported alcohol consumption: The Timeline Followback Interview (TLFB) (Sobel & Sobel) will be administered at the in-person screening and updated at outset of each alcohol drinking session. Participants will be given a blank calendar including memory prompts (e.g., holidays), which covers the designated time interval (the prior 30 days at initial screening) and asked to reconstruct their drinking behavior, cigarette and electronic cigarette usage over that interval. The TLFB has good test-retest reliability and good validity for verifiable events.

Family history of problem drinking: Family history is measured with a subscale taken from the *Addiction Severity Index*.²⁶ Participants are asked to indicate whether or not four classes of relatives on both their mother's and father's side ever "had a significant problem with alcohol or drugs, one that either lead to treatment or should have led to treatment."

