Facets of impulsivity: Impulsivity and risky decision making will be measured using the *UPPS Impulsive Behavior Scale:* a 59-item measure that assesses five subdimensions of impulsivity (premeditation, positive urgency, negative urgency, sensation seeking and perseverance). The *Kirby delay discounting measure*²⁷ and the *Probabilistic Choice Questionnaire (PCQ)*³⁹ will be administered at in-person screening and during alcohol self-administration sessions. The Kirby is a 27-item measure that assesses preferences as to whether participants would prefer smaller, immediate or larger, delayed hypothetical monetary amount. Length of delay and amount of hypothetical funds vary across items. The PCQ is made up of 30 items comparing certain with uncertain hypothetical monetary amounts of varying sizes.

Alcohol purchase task: This is a simulation measure to assess self-reported alcohol consumption and expenditure were alcohol to cost varying amounts of money. The measure generates a number of variables pertaining to reinforcement from alcohol, including intensity of demand.

Physical activity level: The General Practice Physical Activity Questionnaire (GPPAQ)³⁴ a validated physical activity screening tool for patients aged 16-74, will be used to assess physical activity level. This tool generates a simple, 4-level Physical Activity Index (PAI): Active, Moderately Active, Moderately Inactive, and Inactive.

Breath alcohol concentration: Breath alcohol concentration will be assessed using a hand-held Intoxilyzer breathalyzer unit at the in-person screening at outset of each alcohol drinking session and then at several points during the sessions, including determining the point at which participants can be dismissed safely from the session.

Urine drug and pregnancy tests: Urine drug dips will be used to detect opiates, cocaine, phencyclidine, amphetamines, methamphetamine, barbiturates, methadone and benzodiazepines. Urine pregnancy tests will also be administered to all female participants. A positive test for any of the above drugs or a positive pregnancy test will lead to immediate exclusion from the study.

Vital signs (i.e., blood pressure and pulse readings), *height and weight*.

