Administration of alcohol to individuals in treatment for addictive behaviors could potentially impede the progress of their recovery. As a result, we will not enroll individuals who have taken part in inpatient or intensive outpatient treatment for alcohol use or other addictive behaviors in the past 12 months. Further, we will not enroll individuals with a lifetime history of clinically significant withdrawal from alcohol; a lifetime history of medical intervention for withdrawal or who currently present in a manner suggestive of withdrawal, based on the Clinical Institute Withdrawal Assessment for Alcohol (CIWA-Ar). These steps regarding withdrawal will also have the benefit of excluding individuals who are severely dependent on alcohol, for whom alcohol consumption in this study may not be safe. Study activities take place in a controlled, simulated bar lab environment.

Interviews, rating scales and questionnaires: The major risk of the assessments is potential loss of confidentiality, which we address above. To minimize any discomfort associated with reporting sensitive behaviors, participants will be informed that they may refuse to respond to questions that they are not comfortable answering. Questions related to eligibility determination and monitoring of safety and treatment response are not optional. If a person declines to answer these questions, we will advise them that they will not be able to participate.

Confidentiality: Whenever possible, research participants will be referred to by study-assigned ID numbers rather than by their name or other personal information. Accordingly, results of clinical interviews, vital signs, breath alcohol and urine drug/pregnancy screening are recorded by staff members on paper forms using study IDs only. Urine testing will take place only at our research offices. Urine samples will be used for the purposes of this testing only and will be discarded after tests are completed.

However, some private identifiable information about individuals will be collected to enroll and contact participants. This information will be collected primarily via paper forms, which will be stored in locked filing cabinets in a locked room in the research facility in Yon Hall North. This includes a master list connecting participant study identification numbers to participant names.

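### Current alcohol withdrawal is an exclusion judged by the CIWA-Ar, but the scale is stated only for in-person screening and not for the days on which heavy drinkers with alcohol use disorder are given beer

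*Combined protocol and SAP*

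**What the plan says.** The general exclusion criteria in section 6 rule out people who "present with signs of current alcohol withdrawal". Section 8 names the instrument: the study will not enrol those "who currently present in a manner suggestive of withdrawal, based on the Clinical Institute Withdrawal Assessment for Alcohol (CIWA-Ar". In the list of instruments, the CIWA-Ar appears under In-Person Screening (Withdrawal symptoms), where it "will be used to assess severity of current withdrawal syndromes". No section states a second administration, and no CIWA-Ar threshold is given for any visit.

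Under Drinking behaviors in section 6, heavy drinkers must "meet DSM-5 criteria for mild or moderate alcohol use disorder". For the sessions, "Participants will be asked not to drink any alcohol on the day of an alcohol drinking session"; they then receive two beers of about 4.5% alcohol, separated by a 30-minute break. The first session follows screening with no maximum interval. On the second session the plan says: "Participants may be selected for a follow-up appointment for the retest after 1-2 weeks".

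**The concern.** A scale for current withdrawal describes the person on the day it is given. The plan uses it at screening, but the risk it guards against arises when alcohol is consumed. Section 7 makes that link itself: it names current withdrawal as one of the signs of severe dependence that make self-administration in a study potentially unsafe. If the state appears after screening, nothing in the written plan directs staff to look for it before pouring the beer.

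What is at stake is participant safety on session days, mainly for heavy drinkers with alcohol use disorder who have been asked not to drink that day. The comparison of drinking patterns between groups is not at issue.

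**Working it through.** The plan gives no figure to reproduce. The check is a reading of the stated schedule, followed by simple counts.

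**Stated timing of items that can change**

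| Item | Screening | Stated on session day | Where |
|---|---|---|---|
| CIWA-Ar | Yes | No | List of instruments, Withdrawal symptoms |
| Breath alcohol | Yes | Yes | List of instruments, Breath alcohol concentration |
| Timeline followback | Yes | Yes | List of instruments, Self-reported alcohol consumption |
| Menstrual data | Yes | Yes | List of instruments, Menstrual cycle data |
| Pregnancy test | Yes | Yes | Sections 8 and 11 |

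All but the pregnancy repeat sit under the same In-Person Screening heading as the CIWA-Ar, so the heading alone does not imply a repeat. Where one is meant, the text can say so: the timeline followback "will be administered at the in-person screening and updated at outset of each alcohol drinking session", and breath alcohol is measured "at the in-person screening at outset of each alcohol drinking session and then at several points during the sessions". The CIWA-Ar has one stated time point, at screening, and none at either drinking session. The session description, the retest text and the supervision text in sections 8 and 11 mention no withdrawal check before beer is served.

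Vital signs and the SAFTEE symptom list have no visit stated. Some symptom data may therefore exist on session days, but neither item is tied to a rule about withdrawal.

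**Age of the only stated reading**

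Let *g* be the unstated gap in days from screening to session 1.

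- At session 1: *g* days.
- At the retest: *g* + 7 to *g* + 14 days, so at least 7-14 days.

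**Sessions affected** (section 6, Subgroup division and Sample size: four cells of about 10)

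- Heavy drinkers: 2 cells × 10 = about 20.
- One session each: 20 × 1 = 20 exposures.
- All return for the retest: 20 × 2 = 40 exposures.

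The documents give no rate of withdrawal signs in such people, so no event count can be derived.

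**Cost of a same-day check** (the 2-5 minutes per check is an assumption)

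- Checks if given to everyone: 40 × 1 = 40 to 40 × 2 = 80.
- Staff time: 40 × 2 min = 80 min (1.3 h) to 80 × 5 min = 400 min (6.7 h).
- Share of a 3-4 hour session: 2/240 = 0.8% to 5/180 = 2.8%.

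**The case against.** The strongest reply is that the plan does what it says. Withdrawal is written as an enrolment criterion, and screening is where such criteria are checked. Sections 7 and 8 use withdrawal largely as a marker of severe dependence, which is unlikely to change in one or two weeks. Severe alcohol use disorder, medically assisted detoxification and any lifetime history of clinically significant withdrawal are excluded separately. Abstaining on the session day need not be a new challenge either. Screening also proceeds at zero breath alcohol, and the heavy-drinker definition (at least 10 drinks a week, with 1 to 5 binges a week on average) does not require daily drinking. Other changeable items, such as urine drug dips, vital signs and the suicidality interview, also lack a stated repeat. Trained staff supervise, a physician can be consulted, and the check may be done in practice under operating procedures that the documents do not show.

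Much of this stands, and it is why the expected yield is low. The CIWA-Ar is not the only item without a stated repeat, and the documents support only that a recheck is not stated, not that none will be done. The reply does not close the gap, however. Pregnancy is also an eligibility exclusion, and it is rechecked on the day. Exclusions based on history lower the prior risk but do not observe the current state. A breath test does not measure withdrawal, and a zero reading does not rule it out. Supervising staff are given no withdrawal criterion to apply.

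**Conclusion.** The concern holds, as a minor point of participant safety. As written, the exclusion for current withdrawal is checked once before enrolment, and no stated step checks that state when alcohol is given. About 20 heavy drinkers are affected, over about 20 sessions with one each or up to 40 if all return. This assumes full enrolment with cells of about 10; the upper figure also needs every heavy drinker to be invited back and to attend, although the investigators may limit people to one session. Few participants are likely to show signs, and no harm is quantified. The missing threshold is a separate gap in detail that affects screening equally; it matters here because a same-day rule cannot be applied without one.

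**What to change.** Add the CIWA-Ar, with the pulse and blood pressure already listed, to the check-in at the start of each drinking session, beside the breath test and the timeline followback update. The same-day appointment already used for the pregnancy test would serve. Give it to all participants so that check-in is the same in every group. Do not serve alcohol that day to anyone with withdrawal signs, using the same CIWA-Ar threshold as at screening, and state that threshold in the protocol.

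The cost is one protocol line, one stated threshold and a few minutes per session of staff already present, within the 1.3-6.7 hours worked out above. The downside is a slightly longer check-in and an occasional postponed session.
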